6.5.2.1. LY3209590 Dose Initiation and Modification

This section outlines LY3209590

- loading dose (Week 0)
- starting weekly dose (Week 1)
- weekly dose (Weeks 2 to 52)
- dose modification guidance based on hypoglycemia, and
- dose modification guidance based on FBG.

Visit 3 (Week 0 – Randomization) loading dose

At Visit 3 (Week 0), participants randomized to LY3209590 will start study basal insulin therapy.

The LY3209590 **loading dose** is administered at the site and is based on the participant's prior daily basal insulin dose and median FBG from the week prior to randomization (Visit 3 [Week 0]).

Note: If the participant's prestudy basal insulin is **glargine U-300**, the prior daily basal insulin dose should be **reduced by 20%** when determining usual daily basal insulin dose.

For participants with **median FBG \leq 140 mg/dL (7.8 mmol/L)**, follow instructions in this table to calculate the LY3209590 Loading Dose.

LY3209590 Loading Dose – Participants with Median FBG \leq 140 mg/dL (7.8 mmol/L)		
Step	Action	Example Participant A FBG \leq 140 mg/dL (7.8 mmol/L)
1	Determine usual daily basal insulin dose from the lead-in period	24 units/day
2	Calculate Starting Weekly Dose (daily basal dose multiplied by 7 and round to nearest 10)	170 units/week
3	Multiply Starting Weekly Dose by 3 to determine the Loading Dose	510 units Loading Dose

For participants with FBG > 140 mg/dL (7.8 mmol/L), an incremental addition to the prior daily basal insulin dose was instituted to reduce transient hyperglycemia while LY3209590 achieves steady state.

For participants with **median FBG 141 to 160 mg/dL (>7.8 to 8.9 mmol/L)**, the prior daily basal insulin dose should be increased by **10 to 20%**. Follow instructions in this table to calculate the LY3209590 Loading Dose.

LY3209590 Loading Dose – Participants with Median FBG 141 to 160 mg/dL (7.8 to 8.9 mmol/L)		
Step	Action	Example Participant B FBG 141 to 160 mg/dL (>7.8 to 8.9 mmol/L)
1	Determine usual daily basal insulin dose from the lead-in period	24 units/day
2	Increase the usual daily basal insulin dose by 10 to 20% to determine the adjusted daily basal dose	26 units/day
3	Calculate Starting Weekly Dose (adjusted daily basal dose multiplied by 7 and round to nearest 10)	180 units/week
4	Multiply Starting Weekly Dose by 3 to determine the Loading Dose	540 units Loading Dose

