6.5.2.2. Insulin Degludec Dose Initiation and Modification

This section outlines insulin degludec

- dose initiation at Visit 3 (Week 0)
- dose modification guidance based on hypoglycemia, and
- dose modification guidance based on FBG.

Visit 3 (Week 0 – Randomization)

At Visit 3 (Week 0), participants randomized to insulin degludec will start study basal insulin therapy.

The initial degludec dose may be unit-for-unit of the prior basal insulin regimen.

Note: If the participant's prestudy basal insulin is **glargine U-300**, reduce the prior basal insulin dose by **20%**.

Visits 4 to 29 (Weeks 1 to 52)

Titration of the study basal insulin degludec dose should be made at weekly intervals from Weeks 0 to 12 (titration period, Visits 3 to 15), and then at a minimum of every 4 weeks from Weeks 12 to 52 (Visits 16 to 29) or more often as clinically indicated.

Assess hypoglycemia events over the previous week.

Reduce the insulin degludec dose if the participant meets criterion for hypoglycemia dose reduction according to this table.

Hypoglycemia Dose Reduction Criteria	Decrease the Insulin Degludec Dose
2 nocturnal hypoglycemia events ≤ 70 mg/dL ^a (3.9 mmol/L)	
2 fasting hypoglycemia events ≤ 70 mg/dL ^a (3.9 mmol/L)	to previous lower dose ^b
1 nocturnal and 1 fasting hypoglycemia event ≤ 70 mg/dL ^a (3.9 mmol/L)	
Any confirmed severe hypoglycemia	by 2 to 6 units or as clinically indicated

^a Investigator should use discretion to adjust for daytime hypoglycemia that is not attributed to prandial insulin.

^b If there is no previous lower dose, then decrease basal insulin dose by 10% or as clinically indicated.

If the participant does not meet criteria for hypoglycemia dose reduction, determine the median fasting glucose and adjust the insulin degludec dose according to this table.

Insulin Degludec Dose Adjustment			
Median FBG (mg/dL)	Median FBG (mmol/L)	Degludec Dose <15 Units per Day	Degludec Dose ≥ 15 Units per Day
<80	<4.4	Decrease to previous lower dose ^a	Decrease to previous lower dose ^a
80-120	4.4-6.6	No change	No change
121-150	6.7-8.3	Increase by 1 unit	Increase by 2 units
151-180	8.4-10.0	Increase by 2 units	Increase by 3 units
>180	>10.0	Increase by 3 units	Increase by 4 units

^a If there is no previous lower dose, then decrease basal insulin dose by 10% or as clinically indicated.

Source: Adapted from Bartley et al. 2008 and Bolli et al. 2009.

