The table below describes the definition of baseline and postbaseline observations for different analyses.

Analysis	Baseline Observations	Postbaseline Observations
HbA1c (treatment-regimen estimand)	Baseline is the last non-missing assessment prior to or on the day of first dose of study treatment.	Planned measurements at Week 26 (primary endpoint, Visit 22) and Week 52 (secondary endpoint, Visit 29) in EAS1. Use unplanned measurements (on the same visit day) if there are no planned measurements. A multiple imputation approach will be used to impute missing observations at Week 26 (Visit 22) and Week 52 (Visit 29).
HbA1c (efficacy estimand)	Baseline is the last non-missing assessment prior to or on the day of first dose of study.	Weeks 2, 4, 12, 16, 26, 36, and 52 (Visits 5, 7, 15, 17, 22, 25, and 29) in EAS2 for MMRM. All planned measurements at scheduled visits will be included. Use unplanned measurements (on the same visit day) if there are no planned measurements.
CGM parameters (treatment-regimen estimand)	Baseline will be derived from the data collected prior to the first dose of study treatment. A multiple imputation will be used to impute missing observations at baseline.	The CGM values 4 weeks prior to Week 26 (Visit 22) and Week 52 (Visit 29) in EAS1. A multiple imputation approach will be used to impute missing observations at Week 26 (Visit 22) and Week 52 (Visit 29). See detailed derivations in Appendix 6 (Section 6.6).
CGM parameters (efficacy estimand)	Baseline will be derived from the data collected prior to the first dose of study treatment.	The CGM values prior to Weeks 4, 8, 12, 16, 22, 26, 32, 36, 40, 44, 48, and 52 (Visits 7, 11, 15, 17, 20, 22, 24, 25, 26, 27, 28, and 29) in EAS2 for MMRM. See detailed derivations in Appendix 6 (Section 6.6).
Basal insulin dose	The baseline period is the screening/lead-in period prior to the initiation of study treatment. The following variables will be derived: 
• daily dose in U• weekly dose in U, and• dose in U/kg/day. See a detailed derivation of variables in Section 4.4.2.1.	All scheduled visits between Week 0 (Visit 3) and Week 52 (Visit 29) in EAS2 for MMRM. The following variables will be derived: 
• daily dose in U• weekly dose in U, and• dose in U/kg/day See a detailed derivation of variables in Section 4.4.2.1.

Analysis	Baseline Observations	Postbaseline Observations

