Analysis Model	After the imputation, the observed and imputed data will be analyzed by the ANCOVA model using treatment, strata (country, CGM use prior to study entry [yes/no], and carbohydrate counting for prandial insulin dosing [yes/no]), and baseline value of the dependent variable as independent variables. The statistical inference will be based on the multiple imputation framework by Rubin ^b .	The MMRM model will include treatment, strata (country, baseline, CGM use prior to study entry [yes/no], and carbohydrate counting for prandial insulin dosing [yes/no]), and visit and treatment-by-visit interaction as fixed effects and baseline of the dependent variable as a covariate. The Kenward-Roger approximation will be used to estimate denominator degrees of freedom for the MMRM models. An unstructured covariance structure will be used to model the within-participant errors. If this structure fails to converge, the following covariance structures will be used in order until one converges: 
 1. Toeplitz with heterogeneity 2. autoregressive with heterogeneity 3. compound symmetry with heterogeneous variances 4. Toeplitz 5. Autoregressive, and 6. compound symmetry without heterogeneous variances.

Abbreviations: ANCOVA = analysis of covariance; CGM = continuous glucose monitoring; EAS1 = Efficacy Analysis Set 1; HbA1c = hemoglobin A1c; EAS2 = Efficacy Analysis Set 2; MMRM = mixed model of repeated measures.

^a (Qu and Dai 2022)

^b (Rubin 1987)

The 2-sided 95% CI of the LS mean difference (LY3209590 - insulin degludec) in the HbA1c change from baseline to Week 26 (Visit 22) will be estimated. For both estimands, LY3209590 will be declared noninferior to insulin degludec if the upper limit of the 2-side 95% CI for the LS mean difference in the HbA1c (measured in %) change from baseline is below the NIM of +0.4%. In addition, the 95% CI for the LS mean difference will be compared to an alternative NIM of +0.3%.

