4.4.2. Supportive Secondary Endpoints

4.4.2.1. Other Efficacy Endpoints

The analysis of change from baseline for HbA1c at Week 52, fasting glucose by self-monitored blood glucose (SMBG) at Weeks 26 and 52, CGM (except for variability) parameters at Weeks 26 and 52 will be performed for both treatment regimen estimand and efficacy estimand.

For treatment regimen estimand, only participants with an observation at baseline or at the endpoint visit will be included in the analysis. The missing baseline will be imputed using multiple imputation under assumption of missing at random. Missing data at the endpoint visit will be imputed using either retrieved dropout or return-to-baseline multiple imputation approach determined by the criterion described for the primary efficacy endpoint in Section 4.3.2. ANCOVA analysis will be conducted similar to that for the primary endpoint. An additional term of baseline HbA1c stratum ($<8.0\%$, $\geq8.0\%$) will be added into the model for the endpoints other than HbA1c.

For efficacy estimand, participants with baseline and at least 1 post baseline observation will be included in the analysis. The longitudinal observations of actual and change from baseline in HbA1c up to Week 52 will be analyzed using the same MMRM model as for the efficacy estimand described in Section 4.3.2. The analyses of other continuous efficacy measures (insulin dose, fasting glucose, and CGM parameters) will use an MMRM model similar to that for the primary endpoint with an additional term of baseline HbA1c stratum ($<8.0\%$, $\geq8.0\%$). The variance-covariance structure in the MMRM models for fasting glucose from SMBG and insulin dose will be based on compound symmetry.

Additional analyses are as specified below.

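### The insulin-dose MMRMs are fixed to compound symmetry with no fallback or robust variance, so the Week 26 and 52 standard errors for dose are likely to be wrong, in a direction that depends on how the Week 0 loading dose is handled.

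*SAP*

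**What the plan says.** SAP 4.4.2.1 analyses insulin dose with an MMRM modelled on the primary one, plus a baseline HbA1c stratum, and adds that the covariance structure for "fasting glucose from SMBG and insulin dose will be based on compound symmetry". It names no alternative structure and no robust variance.

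The primary MMRM in SAP 4.3.2 is handled differently. There, "An unstructured covariance structure will be used to model the within-participant errors", and six ordered fallbacks follow, the last being "compound symmetry without heterogeneous variances". Its mean model has "visit and treatment-by-visit interaction as fixed effects and baseline of the dependent variable as a covariate"; no baseline-by-visit term is listed.

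On which visits enter, the SAP 4.1 table gives for basal dose: "All scheduled visits between Week 0 (Visit 3) and Week 52 (Visit 29) in EAS2 for MMRM". The rows for bolus dose, total dose and the basal/total ratio start after Week 0, and SAP 4.4.2.1.2 explains why Week 0 is dropped for bolus. Nothing says how the loading dose is treated in the basal-dose analysis.

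On how doses begin, Protocol 6.5.2.2 says "The initial degludec dose may be unit-for-unit of the prior basal insulin regimen". Protocol 6.5.2.1 derives the LY3209590 starting weekly dose from the prior daily dose and then instructs: "Multiply Starting Weekly Dose by 3 to determine the Loading Dose".

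Insulin dose at Weeks 26 and 52 is a listed other secondary endpoint (SAP 1.1). SAP 2.1 applies no multiplicity control to that tier.

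**The concern.** Homogeneous compound symmetry estimates a single residual variance for all visits. With baseline dose in the model, that residual is the spread of dose around what baseline predicts. Early doses are computed largely from the baseline dose. Later doses reflect individual titration, weekly to Week 12 and at least every 4 weeks afterwards, so the spread should widen. Visits 3 to 15 (Weeks 0 to 12) are 13 of the 27 scheduled visits, so they weigh heavily in the pooled variance.

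The standard error at Week 52 would then describe an average visit. Kenward-Roger does not repair this, because it is model-based and takes the covariance structure as correct. Insulin dose has no second analysis to fall back on: the treatment-regimen ANCOVA in SAP 4.4.2.1 covers HbA1c, SMBG fasting glucose and CGM measures, but not dose.

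The Week 0 value adds a separate problem for basal dose. A one-off threefold dose in one arm would enter the same pooled variance.

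**Working it through.** The plan gives no SD, standard error or power for insulin dose, so there is no figure of its own to reproduce. All visit variances below are assumptions.

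**Inputs from the documents.** Visits 3 to 29 give 27 visits: Weeks 0 to 12 weekly, then 14, 16, 18, 20, 22, 24, 26, 28, 32, 36, 40, 44, 48 and 52. Sample size is 284 per arm, the Week 26 completer figure in SAP 5; no Week 52 figure is given.

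**Formula.** With complete data, the compound-symmetry fit gives the treatment difference at visit t the variance (mean of the visit variances) × (1/n1 + 1/n2). Hence:

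- SE ratio (model/true) = √(mean variance / variance at t)
- type I error = 2[1 − Φ(1.96 × ratio)]

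**Assumed variance paths.** For the plateau paths, variance at week w is proportional to 0.01 + 1 − exp(−w/τ).

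| Path | Week 26 ratio | Week 52 ratio | Week 52 type I error |
|---|---|---|---|
| τ = 4, Week 0 in | 0.916 | 0.915 | 7.3% |
| τ = 8, Week 0 in | 0.867 | 0.851 | 9.5% |
| τ = 12, Week 0 in | 0.846 | 0.801 | 11.6% |
| τ = 4, Week 0 out | 0.933 | 0.933 | 6.8% |
| τ = 8, Week 0 out | 0.883 | 0.867 | 8.9% |
| τ = 12, Week 0 out | 0.862 | 0.817 | 11.0% |
| Starts at half the final variance, τ = 8, Week 0 out | 0.944 | 0.935 | 6.7% |
| Linear growth to Week 52 (extreme), Week 0 in | 0.846 | 0.601 | 23.9% |

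Example for τ = 8, Week 0 in: 0.851² = 0.724, so the pooled variance is 72% of the Week 52 variance. Then 1.96 × 0.851 = 1.668 and 2[1 − Φ(1.668)] = 0.095.

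**Loading dose.** A simulation of the compound-symmetry REML fit used 284 per arm and 1,500 runs per scenario. It assumed baseline 25 U/day with SD 10, τ = 8, and a loading dose of three times the rounded weekly dose with a baseline increase of 0, 15% or 25%. Results at Week 52:

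| Final SD of change (U/day) | Ratio, no loading dose | Rejection | Ratio, loading dose kept | Rejection |
|---|---|---|---|---|
| 4 | 0.87 | 8.7% | 1.17 | 2.1% |
| 6 | 0.85 | 9.1% | 0.99 | 5.5% |
| 8 | 0.85 | 8.9% | 0.95 | 6.5% |
| 12 | 0.86 | 9.0% | 0.90 | 8.3% |

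At Week 26 the ratios were 0.86 to 0.90 without the loading dose and 0.92 to 1.19 with it.

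The reason the direction changes can be read from the simulated model standard errors, since pooled variance = SE² × 284/2. At final SD 4 it rises from 0.297² × 142 = 12.5 to 0.409² × 142 = 23.8. At final SD 12 it rises from 0.859² × 142 = 104.8 to 0.904² × 142 = 116.0. The loading dose adds about 11 in both cases. That nearly doubles a small pooled variance and barely moves a large one.

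**The case against.** The case for leaving the SAP alone has several sound parts.

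- Unstructured covariance over 27 visits needs 27 × 28/2 = 378 parameters, whereas the primary list serves a seven-visit HbA1c model. A parsimonious structure chosen in advance is defensible, and SAP 4.6 makes the same choice for its selected laboratory measures. This stands as a reason not to demand unstructured. It does not explain going to equal variances without a robust standard error.
- The wording does not say homogeneous. SAP 4.3.2 lists both forms, so equal variances is the likelier reading but remains an inference.
- The size rests on assumed variances, and the largest effect needs spread to keep growing long after the Week 12 titration period. This stands; the linear path is an extreme case only.

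Four stronger conclusions are tempting, and the documents do not support them.

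- *That dose variance must start near zero and the standard errors must be too small.* This is a fair inference for degludec basal dose. For LY3209590, Week 0 is the loading dose, and the protocol's own three examples turn 24 U/day into 170, 180 or 210 U/week depending on fasting glucose. Bolus and total dose need not start near zero either.
- *That SMBG fasting glucose is affected in the same way.* It shares the covariance sentence but has no near-zero start. Constant variance gives a ratio of 1.00, and variance falling from 1.5 to 1 gives 1.07 at Week 52. It also has a single-visit ANCOVA under the treatment-regimen estimand.
- *That the basal/total ratio model contains Week 0.* SAP 4.1 already starts it after Week 0.
- *That the trial's main conclusions are exposed.* The primary and key secondary tests do not use these models.

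**Conclusion.** The point holds for the insulin-dose MMRMs only. Fixing homogeneous compound symmetry with no fallback or robust variance leaves the Week 26 and 52 intervals for dose dependent on an equal-variance assumption that the titration design makes doubtful.

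Without the loading dose, and under the assumed plateau paths, the Week 52 standard error is probably about 7% to 20% too small. If the loading dose stays in the basal-dose model, as the SAP 4.1 row implies, the ratio ranged from 0.90 to 1.17, so the direction is not determined. A standard error that comes out about right only because a one-off dose offsets an understated variance is not sound inference.

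These figures assume complete data and visit variances that the documents do not give. The consequence is confined to supportive endpoints outside alpha control; the case for changing it is that the remedy costs almost nothing.

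**What to change.** Make two changes to the insulin-dose models in SAP 4.4.2.1 and 4.1, and make them together, because removing the loading dose alone would expose the understated variance.

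1. Either keep compound symmetry as a working structure and base inference on the empirical (sandwich) variance, or use a heterogeneous structure from the SAP 4.3.2 list, such as heterogeneous Toeplitz or heterogeneous compound symmetry, with a stated fallback.
2. Exclude the LY3209590 loading dose from the basal-dose analysis: start that model after Week 0, as SAP 4.1 already does for bolus, total and ratio. Also state that the loading dose does not enter the Week 1 value. SAP 4.4.2.1.2 averages weekly doses since the last visit, which leaves this open.

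The cost is a few lines of SAP text and one procedure option. The sandwich route gives up the Kenward-Roger adjustment, which should matter little with about 284 per arm. The heterogeneous route adds parameters: over 26 visits, heterogeneous compound symmetry needs 26 + 1 = 27 and heterogeneous Toeplitz 26 + 25 = 51, against 26 × 27/2 = 351 for unstructured. If dropout is material, the heterogeneous route is preferable, because the working covariance also governs how missing visits are handled and a sandwich variance does not change that.

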4.4.2.1.1. Analysis for CGM Parameters

The time in glucose ranges will be based on the percentage and time of CGM readings within the glucose ranges, and glucose variability will be based on the readings during the specific CGM period. Appendix 6 (Section 6.6) provides the derivation of CGM parameters.

A longitudinal logistic regression model with independent variables of treatment, strata (country, baseline, CGM use prior to study entry [yes/no], and carbohydrate counting for prandial insulin

dosing [yes/no]), visit and treatment-by-visit interaction and baseline of the dependent variable will be used to analyze the CGM targets of glycemic controls (see Section 6.6.1). The same order mentioned for the MMRM in Section 4.3.2 will be used for the selection of variance-covariance structure.

The time point for primary CGM data analysis is CGM period. In addition, the average time in glucose range, hypoglycemia range, and hyperglycemia range by week (by visit for treatment period) will be summarized by treatment. The average daily time since last dose by CGM period during treatment period will also be summarized for LY3209590. Missing data patterns will be summarized at daily, weekly (visit), and CGM period levels.

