9.3. Statistical Analyses

9.3.1. General Considerations

Statistical analysis of this study will be the responsibility of Lilly or its designees.

Any change to the data analysis methods described in the protocol will require an amendment ONLY if it changes a principal feature of the protocol. Any other changes to the data analysis methods described in the protocol, and the justification for making the change, will be described in the SAP or the clinical study report. Additional exploratory analyses of data will be conducted as deemed appropriate.

Unless otherwise stated, the efficacy analyses will be conducted on either EAS1 or EAS2, and the safety analysis will be conducted on the SS. All tests of treatment effects using statistical models will be conducted at a 2-sided alpha level of 0.05 and 2-sided 95% CI will be provided.

Unless otherwise stated, the other secondary and tertiary efficacy measures will be analyzed on EAS2 using the data up to the discontinuation of LY3209590 or insulin degludec, defined by the date of last study dose +10 days or the initiation of rescue medication whichever is earlier.

Handling of missing, unused, and spurious data are addressed prospectively in the overall statistical methods described in the protocol and in the SAP, where appropriate. Adjustments to the planned analyses are described in the final CSR.

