4.5. Tertiary Endpoint Analysis

4.5.1. Tertiary Efficacy Endpoints

For continuous endpoints, either an ANCOVA model using data from EAS1 or MMRM model using data from EAS2 will be performed as described in Section 4.4.2.1.

For analysis of the binary outcomes, the details are provided in the table below:

Analysis Population	All participants in EAS1 with non-missing baseline measure
Analysis Data	All non-missing observations at baseline and at time point of interest regardless of the use of study intervention or rescue medications.
Endpoint	
 Binary outcome of HbA1c <7% or ≤6.5% at time point of interest with ‘Yes’ indicating achieving HbA1c target. The composite of 
 binary outcome of HbA1c <7% at Week 26, and, binary outcome of no nocturnal level 2 hypoglycemia during treatment phase up to Week 26. The composite of 
 binary outcome of HbA1c <7% at Week 26, and, binary outcome of no level 3 severe hypoglycemia during treatment period up to Week 26 
with “Yes” indicating achieving the target (in respective endpoints defined above).

Missing Data	
 For HbA1c, missing values at the specified timepoints will be imputed using the same method for the primary endpoint (Section 4.3.2). For hypoglycemia that are included in the composite endpoints, a participant who discontinued the treatment period before Week 26 (Visit 22) is considered as a non-responder (that is, experienced the event).
Analysis Model	
These endpoints will be analyzed using a logistic regression model including independent variables of treatment, strata (country, CGM use prior to study entry [yes/no], and carbohydrate counting for prandial insulin dosing [yes/no]), and baseline HbA1c value (and, for the composite endpoint, baseline incidence of hypoglycemia and interaction between baseline HbA1c value and baseline incidence of hypoglycemia. If the model fails to converge, the interaction term will be removed). The unconditional treatment group effect will be assessed based on a robust variance estimator for g-computation estimators (Ye et al. 2023). The estimated treatment group-specific odds ratio, p-value, and 95% CI will be used for treatment comparison. The statistical inference will be based on the multiple imputation framework by Rubin (1987).

Abbreviations: EAS1 = Efficacy Analysis Set 1; HbA1c = hemoglobin A1c.

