The percentage of time within a glucose range (target, hypoglycemia or hyperglycemia ranges) will be calculated as the number of observations within the specified range divided by the number of observations in the time interval (for example, 24-hour period). The average percentage of time among valid CGM days for the corresponding time interval during each analysis visit/period will be used in the analysis.

The duration (in minutes) within the glucose range will then be calculated as the average percentage of time within the glucose range times the length of the period (24-hour, 18-hour, and 6-hour, for the periods of 24-hour, daytime, or nighttime, respectively).

According to the guidance (Battelino et al. 2019), the following CGM targets of glycemic control will also be derived during a 24-hour period:

- The percentage of time within a normal glycemia range (defined as between 70 mg/dL and 180 mg/dL [3.9 and 10.0 mmol/L] inclusive) $>70\%$
- The percentage of time within a hypoglycemia range (defined as <70 mg/dL [3.9 mmol/L]) $<4\%$
- The percentage of time within a hypoglycemia range (defined as <54 mg/dL [3.0 mmol/L]) $<1\%$
- The percentage of time within a hyperglycemic range (defined as >180 mg/dL [10.0 mmol/L]) $<25\%$
- The percentage of time within a hyperglycemic range (defined as >250 mg/dL [13.9 mmol/L]) $<5\%$

In addition, according to the guidance in 2023 (Battelino et al. 2023), 2 composite endpoints will be derived during a 24-hour period:

- $>70\%$ time in range 70 - 180 mg/dL (3.9 - 10.0 mmol/L inclusive) and $<4\%$ time below range <70 mg/dL (<3.9 mmol/L)
- $>70\%$ time in range 70 - 180 mg/dL (3.9 - 10.0 mmol/L inclusive) and $<1\%$ time below range <54 mg/dL (<3.0 mmol/L)

The daily duration (in minutes) of time within a glucose range (defined as <54 mg/dL [3.0 mmol/L]; <70 mg/dL [3.9 mmol/L] and ≥ 54 mg/dL [3.0 mmol/L]; <70 mg/dL [3.9 mmol/L]; ≥ 70 mg/dL [3.9 mmol/L] and ≤ 140 mg/dL [7.8 mmol/L]; ≥ 70 mg/dL [3.9 mmol/L] and ≤ 180 mg/dL [10.0 mmol/L]; >180 mg/dL [10.0 mmol/L] and ≤ 250 mg/dL [13.9 mmol/L]; >250 mg/dL [13.9 mmol/L]) will be merged with the dose administration data to get the summary of daily time in each glucose range since dose administration 4 or 6 weeks prior to the given

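### Read literally, the CGM-target model adjusts for baseline yes/no status and omits the HbA1c stratum; using the measured baseline percentage would be a modest, low-cost gain in efficiency

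*SAP*

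**What the plan says.** SAP Section 6.6.1 defines the outcomes: "the following CGM targets of glycemic control will also be derived during a 24-hour period". It lists five yes/no targets: more than 70% of time at 70-180 mg/dL, less than 4% below 70 mg/dL, less than 1% below 54 mg/dL, less than 25% above 180 mg/dL, and less than 5% above 250 mg/dL. Two composites follow.

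SAP Section 4.4.2.1.1 gives the model: "A longitudinal logistic regression model with independent variables of treatment, strata (country, baseline, CGM use prior to study entry [yes/no" and so on through carbohydrate counting, then "visit and treatment-by-visit interaction and baseline of the dependent variable will be used to analyze the CGM targets of glycemic controls".

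Two neighbouring sections do it differently.
- **Continuous CGM percentages (Section 4.4.2.1).** For the efficacy estimand: "The analyses of other continuous efficacy measures (insulin dose, fasting glucose, and CGM parameters) will use an MMRM model" like the primary one, with the baseline HbA1c stratum added. For the treatment regimen estimand: "An additional term of baseline HbA1c stratum" enters the ANCOVA for endpoints other than HbA1c. The baseline covariate in both is the measured value.
- **Binary HbA1c targets (Section 4.5.1).** The covariates end with "carbohydrate counting for prandial insulin dosing [yes/no]), and baseline HbA1c value", which is the measured value and not baseline target status.

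**The concern.** The baseline term and the strata list match those of the HbA1c MMRM in SAP Section 4.3.2. There they do no harm, because the outcome is continuous and its baseline is a measured HbA1c. Applied to a yes/no outcome, the same wording gives a yes/no baseline covariate and leaves no HbA1c term.

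A participant at 40% time in range and one at 69% are then treated as having the same baseline. The measured percentage separates them, and it is already derived for everyone with valid baseline CGM. What is at stake is precision in the treatment comparisons for the CGM targets, and whether two programmers reading the section would fit the same model.

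**Working it through.** **1. The plan's own figures.** SAP Section 5 gives 670 randomised, 15% dropout, 284 completers per arm, and for continuous time in range a difference of 5 with SD 10.
- Completers: 670 × 0.85 / 2 = 284.75 per arm, in line with the stated 284.
- Standard error: 10 × √(2/284) = 0.839. Power = Φ(5/0.839 − 1.96) = Φ(4.00) = 0.99997, which agrees with the stated figure of at least 99%.

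The documents state no power for the CGM-target models.

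**2. Linear information kept by a yes/no split.** For a normal covariate with a share p above the cut-point c, the share of R² kept is φ(c)² / [p(1−p)]. At p = 0.10, c = 1.282 and φ(c) = 0.1755, so the share is 0.0308/0.09 = 0.34.

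| Share meeting target at baseline | 5% | 10% | 15% | 20% | 25% | 30% | 40% | 50% |
|---|---|---|---|---|---|---|---|---|
| Information kept | 22% | 34% | 43% | 49% | 54% | 58% | 62% | 64% |

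More than half is lost only if fewer than about 21%, or more than about 79%, meet the target at baseline.

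**3. Effect on power.** I simulated a single-visit logistic regression for time in range above 70%, with 3,000 trials per scenario.
- From the documents: 284 per arm, SD 10, the 70% target, and the significance level (Protocol Section 9.3.1: "All tests of treatment effects using statistical models will be conducted at a 2-sided alpha level of 0.05").
- Assumed: normally distributed time in range, a 3-point rise in both arms, baseline attainment of 10%, 20% or 35% (which sets the baseline mean at 70 − 10·z), correlation r of 0.5 or 0.7, and true differences of 2, 2.5, 3 and 5 points.

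Selected results:

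| r | Baseline rate | True difference | No baseline | Yes/no baseline | Measured baseline |
|---|---|---|---|---|---|
| 0.5 | 10% | 3 | 0.706 | 0.733 | 0.770 |
| 0.5 | 20% | 2 | 0.451 | 0.498 | 0.523 |
| 0.5 | 20% | 3 | 0.775 | 0.817 | 0.846 |
| 0.5 | 35% | 3 | 0.803 | 0.844 | 0.862 |
| 0.5 | 10% | 5 | 0.993 | 0.996 | 0.998 |
| 0.7 | 10% | 2.5 | 0.546 | 0.613 | 0.694 |
| 0.7 | 20% | 2 | 0.445 | 0.522 | 0.589 |
| 0.7 | 20% | 3 | 0.791 | 0.870 | 0.920 |
| 0.7 | 35% | 2.5 | 0.648 | 0.760 | 0.824 |
| 0.7 | 10% | 5 | 0.990 | 0.997 | 0.999 |

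Over all scenarios run at 2 to 3 points, the gain from yes/no to measured lies between 0.862 − 0.844 = 0.018 and 0.694 − 0.613 = 0.081. At 5 points both covariates give at least 0.996. The combination r = 0.7 with a 35% rate was obtained only for differences of 2 and 2.5.

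The Monte Carlo standard error of one power figure is at most √(0.25/3000) = 0.009. The smallest gains are therefore imprecise individually, but every scenario with room to gain moved the same way.

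**4. The missing stratum.** Adding a two-level HbA1c stratum (assumed correlation −0.6 between HbA1c and baseline time in range) to the yes/no model changed power by about 1 point at most, for example 0.870 to 0.876 at r = 0.7, 20%, 3 points. Compared with that fuller yes/no model, the measured baseline alone still gains about 2 to 7 points.

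**The case against.** Several points weigh on the other side.

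- **The wording is ambiguous.** The SAP never says the covariate is baseline target status and does not rule out the measured percentage. This stands: the yes/no covariate is the literal reading, not a stated choice. It is also a reason to settle the wording.
- **The missing stratum looks like a slip.** SAP Sections 4.4.2.3.2 and 4.4.2.3.3 give the stratum in full at the same place in the list. A reader might infer a deliberate omission. The documents do not support that, and the simulated effect of the stratum alone is small.
- **A yes/no baseline has precedent here.** Section 4.5.1 uses baseline incidence of hypoglycemia for its composites, and Sections 4.6.3.1.1 and 4.6.3.1.2 use baseline incidence in most logistic models. This stands. Such a covariate is valid under randomisation and better than none (0.870 against 0.791 in one scenario above).
- **The stakes are low.** The targets are not among the endpoints listed in SAP Section 1.1, carry no stated power, and fall outside multiplicity control (Section 2.1). The underlying percentages are analysed as continuous outcomes with the measured baseline. This stands in full.
- **The change is not free.** Low-glucose percentages are skewed and need a chosen functional form. A different covariate set also changes the conditional odds ratio, and Section 4.4.2.1.1 has no g-computation step like that in Section 4.5.1. This stands as a small cost.

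**Conclusion.** The point holds as one of efficiency and clarity, not validity. On its literal wording the model uses a dichotomised baseline and lacks the HbA1c stratum, although a more informative covariate is already derived and the SAP uses the measured baseline for its binary HbA1c targets. For time in range above 70%, the measured baseline gains about 2 to 8 points of power at true differences of 2 to 3 points, and nothing material at 5.

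That range rests on assumed baseline rates, correlations and normality, and on one visit instead of the planned repeated-measures model. The low-glucose targets were not simulated here, so the size of their gain is uncertain.

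A reader might go further and infer that the yes/no covariate throws away most of the baseline information. The documents do not support this as a general statement, because they give no baseline attainment rate. The HbA1c entry range of 7.0-10.0% makes a low rate plausible for time in range above 70%, but does not establish it, and it does not settle the rate for the hypoglycemia targets.

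**What to change.** Amend SAP Section 4.4.2.1.1 in two places before the study team is unblinded.

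1. Replace the outcome's own baseline with the measured baseline CGM percentage for the corresponding glucose range. For skewed low-glucose percentages, prespecify a log or similar transformation, including how zeros are handled. If this model is also meant for the two composites in Section 6.6.1, which the text does not say, state that and enter both component percentages.
2. Replace the stray word *baseline* in the strata list with *baseline HbA1c stratum (<8.0%, ≥8.0%)*, to match the other CGM models.

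This needs no new data. It costs a few lines of text, one prespecified functional form, and an odds ratio that is conditional on a different covariate set. The composites would carry one extra term.
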